When the participants (the index participants) in the HIV self-testing kit group in Aim 1 receive the self-testing kit, they will also be provided 5 referral cards to give to their partners and peers in the drug, sex, and social networks for them to request a free HIV self-testing kit from the IWTK website. On the referral card, a unique code number be used after the subject uses provided URL to land in IWTK website and create an IWTK user account. The unique code number will indicate the IWTK user is referred from an ED patient who is an index participant. The index participants would also be informed of a lottery-based monetary compensation to provide 1 in 10 chance to win an additional \$10 gift card for every IWTK user that is referred from an index participant of our study. Participant who wins the \$10 gift card will be notified via text message, followed by a phone call while participant who does not win the gift card will be notified via text message (see section 20 for "Text Message Script for Lottery Incentive). The confidential code numbers will allow determination of whether ED subjects and/or their referrals use the IWTK website but will not allow research team access to identity-linked test results (Please see data management section below regarding de-identification before data analysis). At the 1-month and 3-month phone follow-up, we will ask participants if they are able to give the referral cards to their partner(s) or friend(s), how many cards they are able to give out, how many cards they are able to give to their partner(s), how many cards they are able to give to their friend(s), and how likely it is that their partner(s) and/or friend(s) will request an HIV self-testing kit from the IWTK website. Finally, we will ask them how we can increase the likelihood of their partner(s) and/or friend(s) accessing the IWTK website and requesting an HIV self-testing kit.

Data management

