- c. Blinding, including justification for blinding or not blinding the trial, if applicable.**
N/A
- d. Justification of why participants will not receive routine care or will have current therapy stopped.**
N/A
- e. Justification for inclusion of a placebo or non-treatment group.**
N/A
- f. Definition of treatment failure or participant removal criteria.**
N/A
- g. Description of what happens to participants receiving therapy when study ends or if a participant's participation in the study ends prematurely.**
N/A

5. Inclusion/Exclusion Criteria

Inclusion Criteria for Aim 1 and 2 "Refusers" Cohort: ED patients who are 18-100 years old, able to provide informed consent for HIV testing, offered an HIV testing by the triage nurse but declined the testing offer.

"High Risk" Cohort; ED patients who are 18-100 years old, able to provide informed consent for HIV testing, who are at increased risk for HIV (i.e. sexually active in the past 12 months, ever injection drug in the lifetime, or men who have sex with men in the life time), those who accept the standard of care (SOC) HIV testing.

For Aim 3: partners or peers of study participants enrolled in the Aim 1.

Exclusion Criteria: Any person who is already known to be HIV positive. Patients with a chief complaint of sexual assault, patients with chief complaint of occupational exposure and patients who are otherwise ineligible to consent to an HIV test due to medical condition (e.g., severe illness, altered mental status). Any person who has previously enrolled in this study. Any person less than 18 years of age. Any person who is not able to provide contact information for follow-up survey. Any person who reports they are unable to access the internet.

6. Drugs/ Substances/ Devices

- a. The rationale for choosing the drug and dose or for choosing the device to be used.**
OraQuick *ADVANCE*® Rapid HIV-1/2 Antibody Test as first FDA-approved HIV test, for which could be purchased over the counter in the US.
- b. Justification and safety information if FDA approved drugs will be administered for non-FDA approved indications or if doses or routes of administration or participant populations are changed.**
N/A.
- c. Justification and safety information if non-FDA approved drugs without an IND will be administered.**
N/A.

7. Study Statistics

a. Primary outcome variable.

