The primary outcome variables include (1) the uptake of HIV self-testing kit among ED patients who decline conventional ED health professional-based HIV testing and to increase the perceived engagement of HIV testing at a regular basis for those with an increased risk for HIV (the index participants); (2) the relative engagement of HIV testing in one month among the index participants with provision of HIV self-testing kit as compared to those without HIV self-testing kit; (3) number of successful referrals for HIV self-testing kit request from the index participants to their partners or peers of their drug, sex, and social network.

b. Secondary outcome variables.

Participant's attitudes and perceptions on conventional health professional HIV testing in the ED as well as home self-testing. Participant's view on his/her partners and peers' attitudes and perceptions on conventional health professional HIV testing in the ED as well as home self-testing.

c. Statistical plan including sample size justification and interim data analysis.

Descriptive data analysis will be performed at the end of the study.

This is a pilot feasibility and acceptability study. We will plan to enroll a total of 200 ED patients (100 in the self-testing group and 100 in the reference group). For 100 participants in the self-testing group, each of them will refer up to 5 partners/peers to IWTK website to request STI screening kit/HIV self-testing kit. Sample size justification is not required. There will be no interim data analysis.

d. Early stopping rules.

N/A

8. Risks

a. Medical risks, listing all procedures, their major and minor risks and expected frequency.

The HIV self-testing kit is an FDA-approved home testing kit which is available over the counter. There should be no medical risks to the participants other than a potential psychological discomforts related to the survey, and if the patients has a positive test result.

b. Steps taken to minimize the risks.

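### Primary outcome 3 is meant to count partners and peers, but a card code shows where the card came from, not who used it, so an index participant's own use can be counted as a referral

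*Combined protocol and SAP*

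**What the plan says.** Section 7a, item (3), defines the outcome as the "number of successful referrals for HIV self-testing kit request from the index participants to their partners or peers of their drug, sex, and social network". Section 5 gives the same Aim 3 population. Neither section says what makes a referral successful.

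Section 4a, Aim 3, describes the measurement. Of kit-group participants it says "they will also be provided 5 referral cards to give to their partners and peers in the drug, sex, and social networks". The recipient goes to the website, opens an account and uses the code. The protocol then states: "The unique code number will indicate the IWTK user is referred from an ED patient who is an index participant". A little later it adds: "The confidential code numbers will allow determination of whether ED subjects and/or their referrals use the IWTK website". It does not say how the two kinds of user are told apart.

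The index participant has a 1 in 10 chance of a $10 gift card "for every IWTK user that is referred from an index participant of our study". At 1 and 3 months the calls ask whether cards could be given out, how many in all, how many to partners and how many to friends. They also ask how likely those people are to request a kit, and how to make that more likely.

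Under Data management in Section 4a, the analyst receives a de-identified IWTK dataset, and participants' identifiers are to be destroyed 3-6 months after enrolment, once follow-up and mailing of incentives are complete. Section 5 excludes "Any person who has previously enrolled in this study", but no step applies this to card users on the website.

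**The concern.** The outcome is about people reached through the index participant's network. The measurement is about cards. The two differ when the card's holder is also its user.

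That is plausible here. Each index participant holds five cards, each good for a free kit, and one aim of the study is testing on a regular basis. The lottery is a weak incentive, but no rule against self-use is stated, so it does not discourage it.

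Aim 3 asks whether referral through drug, sex and social networks is feasible and acceptable. A second kit for the index participant is not network reach, yet it would raise the count that answers that question. The analysis is descriptive and outcome 3 has no comparator, so nothing else in the results would reveal the misclassification.

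**Working it through.** **Inputs from the protocol.** Section 7c plans 100 participants in the self-testing group and states: "For 100 participants in the self-testing group, each of them will refer up to 5 partners/peers to IWTK website". Section 4a gives five cards each and a 1 in 10 lottery for $10 per referred user. The protocol gives no expected number of referrals, no redemption rate and no self-use rate, so there is no planned figure to reproduce.

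**Ceiling.** 100 × 5 = 500 cards.

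**Incentive.** Expected value per coded user: 0.1 × $10 = $1. For all five cards: 5 × $1 = $5.

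**Illustrative size.** Let T be true partner or peer referrals and F index participants' own uses. The false share of the reported count is F/(F + T), and the overstatement relative to the truth is F/T. The values below are assumptions: F = 0, or 5 to 20 (5-20% of 100 index participants using one card each); T = 25 (5% of 500 cards) or 100 (20%).

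| T | F | Reported count | False share | Overstatement |
|---|---|---|---|---|
| 25 | 0 | 25 | 0% | 0% |
| 25 | 5 | 30 | 5/30 = 17% | 5/25 = 20% |
| 25 | 20 | 45 | 20/45 = 44% | 20/25 = 80% |
| 100 | 0 | 100 | 0% | 0% |
| 100 | 5 | 105 | 5/105 = 5% | 5/100 = 5% |
| 100 | 20 | 120 | 20/120 = 17% | 20/100 = 20% |

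**Could the described data separate F from T?**

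- *Kit access information.* Index participants report results using information packed with the kit (Section 4a, HIV Self-testing at home). That identifies them on that route. It does not identify one who opens an account with a card code.
- *Call questions.* Cards reported as given out can be compared with coded requests, which is a partial check. It fails when fewer cards are redeemed than given. Suppose a participant gives out three cards, one friend redeems, and the participant uses a fourth card personally. That makes two coded requests against three cards given, and nothing looks wrong.
- *Timing.* After de-identification and destruction of identifiers, accounts cannot be matched to participants and participants cannot be asked.

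**The case against.** The strongest reply is that the protocol nowhere says every coded user is counted. A reader might infer such a rule from the sentence on the code, but outcome 3 and the Aim 3 population are both limited to partners or peers, and self-use fits neither wording. The sentence on ED subjects and their referrals may also reflect an intention to separate the two. This stands as far as it goes: the counting rule is unspecified rather than wrong. But a restriction in the wording does not help if the data cannot apply it, and no way of applying it is described.

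A reader might also infer that a card used by a reference-group patient is a false referral. The documents do not support that. Such a patient may be a real partner or peer and so fit Aim 3, and it is not stated whether the previous-enrolment exclusion reaches Aim 3. What remains is kit exposure in the comparator for outcome 2.

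Nor can self-redemption be called the only objective sign of repeat testing. Section 3 describes another route to a free HIV kit through IWTK, index participants can report results on the website, and Section 7a words the regular-testing outcome as perceived engagement.

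Three further points stand. The full phone script and the separate IWTK protocol are not available here, so an own-use question or a block on duplicate accounts may exist. The rates are assumed. And this is a 200-person descriptive pilot with no test or threshold resting on the count. That limits the severity, but a descriptive count depends entirely on its case definition.

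**Conclusion.** The concern holds in a limited form. As described, the measurement of outcome 3 cannot distinguish an index participant's own card use from a referral, and the plan sets no rule for handling it. Under the assumed 5 to 20 self-uses, the false share of the count runs from 5% (100 true referrals, 5 self-uses) to 44% (25 true referrals, 20 self-uses). If nobody self-uses it is zero, but the planned data could not show that. These figures illustrate sensitivity and do not predict what will happen.

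The conclusion rests on the procedures written in the protocol and on the call questions it lists. It would weaken if the phone script or IWTK procedures already identify self-use. The change is worth making because it is cheap, concerns a named primary outcome, and cannot be made after identifiers are destroyed.

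**What to change.** 1. **Define the outcome.** State in Section 7a that outcome 3 is coded HIV-kit requests, one per person, excluding index participants' own use. Report own use separately as repeat kit requests, and do not let it earn the referral lottery.
2. **Ask.** Add one item per arm to the existing 1- and 3-month calls. Kit arm: *Did you use any of the cards to order a kit for yourself?* (recording how many). Reference arm: *Did you get a study card or kit from anyone?*
3. **Report reference-group use separately.** Give coded requests by reference patients their own line and flag them as kit exposure for outcome 2. Do not remove them as false referrals.
4. **Match, if the IRB allows.** Before de-identification, and before participants' identifiers are destroyed, the IWTK data manager compares coded accounts with the enrolment list and passes on only a match flag. No test results are needed.

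**Cost.** One call item per arm and a few lines of outcome wording. Matching may need IRB review, because it uses account details held under a separate protocol. Without matching, the correction relies on self-report and misses participants not reached by phone. The reported referral count may be lower.

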One approach to narrowing the testing gap is to offer HIV self-testing, which offers an alternative innovative approach outside of the traditional modes of engaging patients, with potential to reach difficult to reach populations. Self-testing at home decreases the stigma and privacy barriers associated with a conventional health professional-based testing model, and may significantly increase HIV testing uptake, thereby potentially decreasing the number of undiagnosed HIV.¹⁰ Many partners and peers of individuals at risk for HIV are also hard-to-reach population.¹¹ Network snowballing recruitment approach has successfully used to identify persons with undiagnosed HIV infection.¹²⁻¹⁶ This approach will significantly improve the participation and involvement of those hard-to-reach high risk populations.

First, we hypothesize that the provision of an HIV self-testing kit to ED patients who decline conventional ED-based HIV testing will be acceptable for these “refusers” and this approach will increase the uptake and engagement of overall HIV testing. Second, we hypothesize that the provision of an HIV self-testing kit to ED patients who are at increased risk for HIV will be acceptable and will increase the engagement of HIV testing at regular basis. We also hypothesize that partners and peers of the testing “refusers” or ED patients with increased risk for HIV will request an HIV self-testing kit for HIV testing if they are referred by their partners or friends.

2. Objectives (include all primary and secondary objectives)

The proposed pilot research has three aims: 1) to determine the feasibility and acceptability of provision of HIV self-testing kit (OraQuick *ADVANCE*® Rapid HIV-1/2 Antibody Test) in order to increase uptake and engagement of HIV testing among ED patients who decline conventional ED health professional-based HIV testing and to increase the engagement of HIV testing at a regular basis for those with an increased risk for HIV (the index participants); 2) to determine the uptake and engagement of HIV testing by provision of HIV self-testing kit; and 3) to determine the feasibility and acceptability of HIV self-testing kit referral among partners or peers of the index participants through drug, sex, or social networks.

3. Background (briefly describe pre-clinical and clinical data, current experience with procedures, drug or device, and any other relevant information to justify the research)

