HIV testing is recommended for all individuals aged 13-65 years.¹ Recent CDC data indicate that > 50% of Americans aged 18-64 years report never having been testing for HIV.^{17,18} They could be those who are unengaged with conventional health professional based testing at the medical care setting such as emergency departments (EDs) where the HIV testing decline rate is up to 50 - 60%.^{8,9} Or, they could be disfranchised hard-to-reach populations who are much less accessible to health care.

HIV seroprevalence in JHH ED patients increased from 5.2% in 1987 to 11% in the early 2000s and decreased to 7.8% in 2007 and 5.6% in 2013 (eIRB protocol NA_00027191, NA_00085477). An ED HIV testing program was implemented in the JHH ED in 2005, where it continues today (eIRB protocol - NA_00044965, *Rapid On-Site HIV Testing in the Emergency Department (ED)*). Currently, up to 50 to 60% of JHH ED patients decline to be tested when non-targeted offering of HIV testing is made available to all patients (IRB00051816).

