Aim 1 & 2: (to determine the feasibility and acceptability take-home HIV self-testing kits (OraQuick ADVANCE® Rapid HIV-1/2 Antibody Test) in order to increase uptake and engagement of HIV testing among ED patients who decline conventional ED health professional-based HIV testing and to increase the engagement of HIV testing at a regular basis for those with an increased risk for HIV (the index participants); 2) to determine the uptake and engagement of HIV testing by provision of HIV self-testing kit)

We will conduct a pilot randomized study at JHH ED on patients who decline routine HIV testing offer by triage nurses.

1. Recruitment

“Refusers” Cohort

Study staff will screen the ED tracking board (Epic) for patients who meet study enrollment criteria, which is done routinely as part of the ED HIV testing program. When an eligible patient is identified by the chart review (please see HIPAA form 4), the study staff will talk to the ED clinician regarding research opportunity for the potentially eligible patients. For all individuals who are not clinical patients of a study team member, the recruitment procedure will be that the patient's clinician will request and document in the chart the patient's permission to be contacted by the research staff.

“High Risk” Cohort

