“The eligibility of “high-risk cohort” is ED patients who are offered an HIV test as the standard of care in the ED, accept the standard of care (SOC) HIV testing, and who have at increased risk for HIV. Study staff will screen the ED tracking board (Epic) for patients who are offered an HIV test at triage by the triage nurse, which is done routinely as part of the ED HIV testing program. When an eligible patient is identified by the chart review (please see HIPAA form 4), the study staff will talk to the ED clinician regarding research opportunity for the potentially eligible patients. For all individuals who are not clinical patients of a study team member, the recruitment procedure will be that the patient's clinician will request and document in the chart the patient's permission to be contacted by the research staff. In order to determine if the patient is at increased risk for HIV, the study staff will use of the Screening Question (three screening questions) that is uploaded in eIRB application section 20 (see section 20 for Screening_Question_05312016”). The three questions are as follows: 1) Have you been sexually active in the past 12 months, 2) have you ever used injection drugs in your life, and 3) (for men only), have you ever had sex with a man in your life time. If the patient responds “yes” to the question “Is any of your answer “Yes” (see section 20 for Screening_Question_05312016”)?, they will be considered eligible and will then go through the consent and enrollment procedures. **No identifiers will be collected for this screening step.**

2. Enrollment

The study staff will obtain verbal informed consent. The process will involve a description of the study as provided in the verbal consent form (OralConsentScript_for_HighRiskPatient_06012016.docx) with a chance to provide answers to any questions about the study. Justification for verbal consent is provided in the e-IRB application. Specifically, this study involves no bodily intervention and poses minimal risk to patients. The consent process will take between approximately 5-10 minutes, but as much time as needed will be provided to patients. Consented subjects will be given a copy of the oral

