consent document for their information and records. In this consent, the patient will be asked for permission to review their medical charts at Johns Hopkins Hospital for the clinical information of their ED visit. Consented patients will be randomized to one of two groups, the Index Group (Group 1) or the Reference Group (Group 2). The index group or the HIV self-testing kit group will be provided a free FDA-approved HIV self-testing home kit (OraQuick *ADVANCE*® Rapid HIV-1/2 Antibody Test) and the reference group will not receive the HIV self-testing kit. Consented patients in both groups will fill out a short survey regarding their socio-demographic information as well as their experience, attitudes, and perceptions regarding HIV testing. For patients who are in the HIV self-testing kit group, they will be asked if they would like to take a free FDA-approved HIV self-testing home kit home. If they agree, the research staff will make sure the patients will take the kit home when they are discharged. Participants in this group will also receive information regarding how to access the IWTK website to report the completion of HIV self-testing at home. Participants in this group will also be informed of a lottery-based monetary compensation with 1 in 10 chance to win an additional \$50 gift card for reporting the test results to the IWTK website. Participant who wins the \$50 gift card will be notified via text message, followed by a phone call while participant who does not win the gift card will be notified via text message (see section 20 for "Text Message Script for Lottery Incentive). For patients who are in the reference group, a standard pamphlet regarding the importance of HIV testing and HIV testing venues in Baltimore City used by current JHH ED-based HIV testing program will be provided to the patients.

3. Survey information:

- Patients will be consented and enrolled in the study prior to collecting data in the ED.

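### Must the plan add counts of refusers screened, approached and consenting before its kit-uptake outcome can be interpreted?

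*Combined protocol and SAP*

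**What the plan says.** The first hypothesis in section 1 (Abstract) is that "provision of an HIV self-testing kit to ED patients who decline conventional ED-based HIV testing will be acceptable" to them. Section 7a makes the first primary outcome "the uptake of HIV self-testing kit among ED patients who decline conventional ED health professional-based HIV testing". The same sentence goes on to the high-risk cohort and closes with a parenthesis naming the index participants. No denominator is given. Section 7c plans a descriptive analysis of 200 patients, 100 per group, without a split by cohort.

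Section 3 (Background) reports that "up to 50 to 60% of JHH ED patients decline to be tested". For the refuser cohort, section 4a (Recruitment) says: "Study staff will screen the ED tracking board (Epic) for patients who meet study enrollment criteria". There is then a permission step. "For all individuals who are not clinical patients of a study team member", the patient's "clinician will request and document in the chart the patient's permission to be contacted by the research staff". Section 5 excludes people who cannot give contact information or cannot access the internet. Under section 4a (Enrollment), consent comes before randomisation, and only in the kit group is it the case that "they will be asked if they would like to take a free FDA-approved HIV self-testing home kit home".

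On record keeping before consent, the only explicit statement concerns the three risk questions for the high-risk cohort: "No identifiers will be collected for this screening step". Chart abstraction is described as following enrolment. The attachments cited as section 20 and HIPAA form 4 are not part of the available text.

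**The concern.** The hypothesis is about patients who turn down a test in the emergency department. The people in whom uptake is measured have passed a permission step, two practical exclusions and a consent discussion. Someone who has just refused one offer may well refuse the next, so permission and consent are plausible points of selection. If those who enrol take kits more readily than those who do not, the kit-group rate would overstate acceptability among refusers in general; if less readily, it would understate it.

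Feasibility and acceptability are Aim 1, so the share of refusers who can be enrolled is a natural pilot result in itself. Counts not kept during recruitment may be hard to rebuild. The stake is the breadth of the conclusion on outcome 1. The randomised comparison in outcome 2 is not biased internally by selection before randomisation.

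**Working it through.** **1. Which population does outcome 1 name?** Four places bear on this.

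- Section 2, Aim 1 lists refusers and high-risk patients and closes with the label index participants. Section 7a, outcome 1 follows the same pattern.
- Section 7a, outcome 2 uses the label for people with and without a kit, that is, for both randomised groups.
- Section 4a, Aim 3 uses it for kit-group participants who receive a kit and referral cards.
- Section 5 describes the Aim 3 population as partners or peers of participants enrolled in Aim 1, where section 2 says partners or peers of the index participants.

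Every clear use refers to enrolled people. The parenthesis in outcome 1 could be read as attaching only to the high-risk clause. But the third hypothesis in section 1 speaks of partners and peers of both refusers and high-risk patients, so the label most naturally covers both cohorts. On that reading outcome 1 matches what is measured, and only the wording of the first hypothesis is broader.

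**2. How large could the gap be?** The plan states no figure to reproduce. Let u be uptake among refusers in the kit group, c the share of eligible refusers who enrol, and v the uptake the others would have had. The documents give none of these; all values below are assumptions.

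Uptake in all eligible refusers = c·u + (1 − c)·v. With v anywhere from 0 to 1, the range is c·u to c·u + (1 − c), with width 1 − c.

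| c | u = 80% | u = 50% | width |
|---|---|---|---|
| 10% | 8% to 98% | 5% to 95% | 90 points |
| 30% | 24% to 94% | 15% to 85% | 70 points |
| 50% | 40% to 90% | 25% to 75% | 50 points |
| 70% | 56% to 86% | 35% to 65% | 30 points |

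The kit-group rate minus the rate in all eligible refusers is (1 − c)(u − v). At c = 50% and u = 80% it lies between 0.5 × (0.8 − 1) = −10 points and 0.5 × (0.8 − 0) = +40 points. If v = u it is zero.

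**3. Would reporting those bounds help?** The share 1 − c mixes two groups: refusers who were approached and said no, and refusers nobody approached because staff were absent or the target of 200 had been met. Write c = a × k, where a is the share approached and k the share of those who consent. If a = 20% and k = 50%, then c = 0.2 × 0.5 = 10%. At u = 80% the bounds are then 8% to 98% for all eligible refusers, but 0.8 × 0.5 = 40% to 0.4 + 0.5 = 90% for those approached. The extra 40 points of width (90 − 50) reflect staffing and a fixed target, not refusal. With up to 50 to 60% of patients declining and only 200 to be enrolled across both cohorts, a low c is quite possible.

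Two further limits apply. Taking people without internet or contact details out of the denominator leaves the bounds silent about them, although they are part of the gap between enrolled refusers and refusers in general. And an identifier-free tally counts visits, not people. Section 5 excludes people who enrolled before, so return visits are foreseen; repeated counting of the same non-enrolled refuser would lower c artificially.

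**4. What can be reported from the plan as it stands?** Randomisation does not select among those who consent, so kit takers divided by refusers randomised to the kit group is a valid rate for enrolled refusers. If 50 refusers fell in that group (an assumption) and 40 took kits, the rate would be 80% with an exact 95% interval of 66.3% to 90.0%. Charted permissions and the number enrolled would also give enrolled over permitting, for patients who go through the permission step.

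**The case for a change.** The strongest case for a change is that acceptability to refusers is the reason for the study, and a tally is cheap. Staff already screen the tracking board, no identifiers are needed, and neither design nor sample size would alter. Calling the study a pilot excuses the absence of a sample size calculation; it does not excuse losing recruitment counts when feasibility is the aim. Recovery afterwards would be partial: charted permission need not show who refused permission, and nothing in the available text provides for recording refusals of consent or exclusions for internet access.

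Much of that stands as advice on good reporting. A careful report would state the uptake denominator, give the numbers approached and consenting, and confine its conclusion to eligible refusers who consented. It does not show an error in the plan. No stated number, rule or analysis would be corrected, and the descriptive analysis in section 7c already leaves room for these figures. Nor is the absence of a log established, since the section 20 attachments and HIPAA form 4 are not available, and the fixed headings of the form do not ask for participant flow. If no log was kept, the consequence is a narrower conclusion, which is what the design supports in any case.

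**Conclusion.** No change to the plan is needed. Outcome 1 most likely refers to enrolled participants, and for them the kit-group rate is sound; outcome 2 is unaffected. What remains is the usual limit that consent places on generalising, together with an unwritten denominator and log that analysts of a feasibility pilot would normally supply.

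The possible gap between enrolled refusers and all eligible refusers is not small in the worst case: −10 to +40 points at an assumed 50% enrolled and 80% uptake. But its direction and size are unknown, it may be zero, and the bounds that would express it could be almost empty (8% to 98% at an assumed 10% enrolled).

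The conclusion rests on reading index participants as enrolled people in both cohorts, and on the eventual report limiting its claim to eligible refusers who consented.
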